## 14.11.8. Safety Figures

Safety: Figures						
StInt No.	SAC No.	Population	IDSL / Example Shell	Title	Programming Notes	Deliverable [Priority]
Adverse Events						
	3.1	mITT	AE10	Plot of Common ( $\geq 5\%$ ) On-Treatment Adverse Events and Relative Risk	IDSL One page per active treatment compared to placebo Include AEs which have $\geq 5\%$ incidence in any treatment group	SAC
Laboratory						
3.1	3.2	mITT	LIVER14	Scatter Plot of Maximum Post-Baseline vs. Baseline for ALT	IDSL	StInt, SAC
3.2	3.3	mITT	LIVER9	Scatter Plot of Maximum Post-Baseline ALT vs. Maximum Post-Baseline Total Bilirubin	IDSL	StInt, SAC
3.3	3.4	mITT		Plot of Mean (95% CI) Neutrophil Counts over Time		StInt, SAC
	3.5	mITT		Plot of Mean (95% CI) Neutrophil Counts over Time for Subjects with Pneumonia		Post SAC
Spirometry						
	3.6	mITT		Mean (90% CI) Post-Bronchodilator FEV1 (L) over Time	Baseline, Day 84 and 168	Post SAC
3.4	3.7	mITT		Adjusted Mean (90% CI) Change from Baseline Post-Bronchodilator FEV1 (L) over Time		StInt, SAC
	3.8	mITT		Mean (90% CI) Post-Bronchodilator FVC (L) over Time	Baseline, Day 84 and 168	Post SAC
3.5	3.9	mITT		Adjusted Mean (90% CI) Change from Baseline Post-Bronchodilator FVC (L) over Time		StInt, SAC

Safety: Figures						
StInt No.	SAC No.	Population	IDSL / Example Shell	Title	Programming Notes	Deliverable [Priority]
	3.10	mITT		Mean (90% CI) Post-Bronchodilator FEV1/FVC Ratio over Time	Baseline, Day 84 and 168	Post SAC
ECG						
3.6	3.11	mITT		Boxplot of Change from Baseline in QTcF by Time and Treatment		StInt, SAC

**14.11.9. Pharmacokinetic Tables**

SAC No.	Population	IDSL / Example Shell	Title	Programming Notes	Deliverable [Priority]
4.1	PK	PKCT1	Summary of Danirixin Whole Blood Pharmacokinetic Concentration-Time Data (Dry Blood Spot)	Include geometric mean and 90% CI for the summary of blood concentration data	SAC
4.2	PK	PKPT4	Summary of Derived Danirixin Whole Blood Pharmacokinetic Parameters (Dry Blood Spot)		SAC
4.3	PK2	Table 3.10 Study 201037	Summary of Statistical Analysis of Log-Transformed Danirixin Concentration-Time Data Dry Blood Spot vs Wet Whole Blood Samples - Bland Altman Analysis		SAC
4.4	PK2	Table 3.12 Study 201037	Summary of Statistical Analysis of Log-Transformed Danirixin Pharmacokinetic Parameters Dry Blood Spot vs Wet Whole Blood Samples - Bland Altman Analysis		SAC
4.5	PK2	Table 3.11 Study 201037	Summary of Statistical Analysis of Log-Transformed Danirixin Pharmacokinetic Parameters Dry Blood Spot vs Wet Whole Blood Samples		SAC

SAC No.	Population	IDSL / Example Shell	Title	Programming Notes	Deliverable [Priority]
4.6	PK2	Table 3.10 Study 201037	Summary of Statistical Analysis of Log-Transformed Danirixin Concentration-Time Data Sensitivity Analysis: Dry Blood Spot vs Wet Whole Blood Samples - Bland Altman Analysis	excluding dry blood spot concentrations above the assay HLOQ of 1000 ng/mL	SAC
4.7	PK2	Table 3.12 Study 201037	Summary of Statistical Analysis of Log-Transformed Danirixin Pharmacokinetic Parameters Sensitivity Analysis: Dry Blood Spot vs Wet Whole Blood Samples - Bland Altman Analysis	excluding dry blood spot concentrations above the assay HLOQ of 1000 ng/mL	SAC
4.8	PK2	Table 3.11 Study 201037	Summary of Statistical Analysis of Log-Transformed Danirixin Pharmacokinetic Parameters Sensitivity Analysis: Dry Blood Spot vs Wet Whole Blood Samples	excluding dry blood spot concentrations above the assay HLOQ of 1000 ng/mL	SAC

**14.11.10. Pharmacokinetic Figures**

SAC No.	Population	IDSL / Example Shell	Title	Programming Notes	Deliverable [Priority]
4.1	PK	PKCF1p	Individual Whole Blood Danirixin Concentration-Time Plots by Subject (Linear and Semi-log) (Dry Blood Spot)	1. X-axis displays actual relative time 2. Include line for LLQ along with footnote defining LLQ value 3. Include values below LLQ 4. Overlay Visit 3, 6, 7 and 10.	SAC
4.2	PK	PKCF6	Individual Whole Blood Danirixin Concentration-Time Plots by Day (Linear and Semi-log) (Dry Blood Spot)	1. X-axis displays actual relative time 2. Include line for LLQ along with footnote defining LLQ value 3. Include values below LLQ	SAC

**CONFIDENTIAL**

205724

SAC No.	Population	IDSL / Example Shell	Title	Programming Notes	Deliverable [Priority]
4.3	PK	PKCF4	Mean ( $\pm$ SD) Whole Blood Danirixin Concentration-Time Plots (Linear and Semi-log) (Dry Blood Spot)	1. Include the full SD bars at each time point 2. X-axis displays planned relative time 3. Include line for LLQ along with footnote defining LLQ value 4. Overlay Visit 3, 6, 7 and 10.	SAC
4.4	PK	PKCF5	Median (Range) Whole Blood Danirixin Concentration-Time Plots (Linear and Semi-log) (Dry Blood Spot)	1. Include bars for range at each time point 2. X-axis displays planned relative time 3. Include like for LLQ along with footnote defining LLQ value 4. Overlay Visit 3, 6, 7 and 10.	SAC
4.5	PK	PK27	Median (Range) Pre-Dose Whole Blood Danirixin Concentration Versus Day (Linear and Semi-log) (Dry Blood Spot)	1. Include bars for range at each time point 2. X-axis displays Visit 3. Include like for LLQ along with footnote defining LLQ value 4. Visit include 3, 6, 7 and 10.	SAC
4.6	PK	Figure 11.206 Study 200163	Individual Whole Blood Pharmacokinetic Parameters (+Geometric Mean and 95% CI) versus Demographics	Demographics: Age, Weight, Gender. By day.	SAC
4.7	PK		Scatter Plot of Whole Blood Danirixin Concentration-by Day (Dry Blood Spot)		Post SAC
4.8	PK2	Figure 3.10 Study 201037	Individual Subject Danirixin Blood Concentration-Time Plot (Linear and Semi-Log) by Subject Dry Blood Spot vs Wet Whole Blood Samples		SAC

**CONFIDENTIAL**

205724

SAC No.	Population	IDSL / Example Shell	Title	Programming Notes	Deliverable [Priority]
4.9	PK2	Figure 3.8 Study 2010137	Comparative Plot of Individual Subject Danirixin Blood Concentrations Dry Blood Spot vs Wet Whole Blood Samples		SAC
4.10	PK2	Figure 3.9 Study 201037	Bland-Altman Plot of Individual Subject Log-Transformed Danirixin Blood Concentrations Dry Blood Spot vs Wet Whole Blood Samples		SAC
4.11	PK2	Figure 3.10 Study 201037	Individual Subject Danirixin Blood Concentration-Time Plot (Linear and Semi-Log) by Subject Sensitivity Analysis: Dry Blood Spot vs Wet Whole Blood Samples	excluding dry blood spot concentrations above the assay HLOQ of 1000 ng/mL	SAC
4.12	PK2	Figure 3.8 Study 2010137	Comparative Plot of Individual Subject Danirixin Blood Concentrations Sensitivity Analysis: Dry Blood Spot vs Wet Whole Blood Samples	excluding dry blood spot concentrations above the assay HLOQ of 1000 ng/mL	SAC
4.13	PK2	Figure 3.9 Study 201037	Bland-Altman Plot of Individual Subject Log-Transformed Danirixin Blood Concentrations Sensitivity Analysis: Dry Blood Spot vs Wet Whole Blood Samples	excluding dry blood spot concentrations above the assay HLOQ of 1000 ng/mL	SAC

## 14.11.11. Pharmacokinetic / Pharmacodynamic Figure

Pharmacokinetic / Pharmacodynamic: Figures					
SAC No.	Population	IDSL / Example Shell	Title	Programming Notes	Deliverable [Priority]
5.1	PK		Scatter plot of PD endpoint versus Danirixin Concentration (Trough)	CAT Total Score Include Placebo imputed as DNX conc=0ng/mL, include DNX conc=NQ imputed as LLOQ/2, where LLOQ=5ng/mL By Day Different symbol for each treatment	Post SAC
5.2	PK		Scatter plot of Safety versus Danirixin Concentration (Trough)	Blood Neutrophil Count and C-reactive Protein (CRP) Highlight subjects with an on-treatment event in the 'Infective pneumonia' SMQ. Add footnote 'Note: Pneumonia may have occurred at any time during the study' Include Placebo imputed as DNX conc=0ng/mL, include DNX conc=NQ imputed as LLOQ/2, where LLOQ=5ng/mL By Day Different symbol for each treatment	Post SAC
5.3	PK		Quartile plot of Danirixin Concentration versus PD endpoint	CAT Total Score	Post SAC
5.4	PK		Quartile plot of Danirixin Concentration versus Safety endpoint	Blood Neutrophil Count and C-reactive Protein (CRP)	Post SAC

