9.4.5. Pneumonia

All suspected pneumonias will require confirmation as defined by the presence or new infiltrate(s) on chest x-ray AND at least 2 of the following signs and symptoms:

- Increased cough
- Increased sputum purulence (colour) or production
- Auscultatory findings of adventitious sounds (e.g. egophony, bronchial breath sounds, rales, etc.)
- Dyspnea or tachypnea
- Fever (oral temperature > 37.5 °C)
- Elevated white blood cell count (WBC) (> 10 x 10⁹/L or > 15% immature forms)
- Hypoxemia (Hb O₂ saturation < 88% or at least 2% lower than baseline value)

All pneumonias must be captured on the AE/SAE page of the eCRF and on the pneumonia page of the eCRF.

The Investigator and site staff should remain vigilant for the possible development of pneumonia in participants as the clinical features of such infections overlap with the symptoms of COPD exacerbations. For all suspected cases of pneumonia, Investigators are strongly encouraged to confirm the diagnosis (this includes obtaining a chest x-ray) and to initiate appropriate therapy as promptly as possible. Any microbiology or virology tests performed to determine etiology should be reported on the pneumonia eCRF page. All diagnoses of pneumonia (radiographically confirmed or unconfirmed) must be reported as an AE or SAE (if applicable).

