## 11. BIOMARKER ANALYSES

C-reactive protein and fibrinogen data will be summarized in the same way as laboratory data. Summary tables and boxplots for each treatment by visit (including screening, baseline, Day 84 and Day 168) will be generated for the mITT populations and also for the subset of subjects who have an event in the 'Infective pneumonia' SMQ.

Exploratory biomarker analysis will be the subject of a separate RAP.

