14.11.12. Biomarker Tables

Biomarker: Tables						
StInt No.	SAC No.	Population	IDSL / Example Shell	Title	Programming Notes	Deliverable [Priority]
Biomarkers						
6.1	6.1	mITT	LB1	Summary of C-reactive Protein (CRP) Changes from Baseline	ICH E3	StInt, SAC
6.2	6.2	mITT	LB1	Summary of Fibrinogen Changes from Baseline	ICH E3	StInt, SAC
	6.3	mITT		Summary of C-reactive Protein (CRP) for Subjects with Pneumonia	Screening, Baseline, Day 84 and 168 Subjects who have an event in the 'Infective pneumonia' SMQ	Post SAC
	6.4	mITT		Summary of Fibrinogen for Subjects with Pneumonia	Screening, Baseline, Day 84 and 168 Subjects who have an event in the 'Infective pneumonia' SMQ	Post SAC

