## 14.11.13. Biomarker Figures

Biomarker: Figures						
StInt No.	SAC No.	Population	IDSL / Example Shell	Title	Programming Notes	Deliverable [Priority]
Biomarkers						
6.1	6.1	mITT		Boxplot of C-reactive Protein (CRP) by Time and Treatment	Screening, Baseline, Day 84 and 168	StInt, SAC
6.2	6.2	mITT		Boxplot of Fibrinogen by Time and Treatment	Screening, Baseline, Day 84 and 168	StInt, SAC
	6.2	mITT		Boxplot of C-reactive Protein (CRP) over Time for Subjects with Pneumonia	Screening, Baseline, Day 84 and 168 Subjects who have an event in the 'Infective pneumonia' SMQ	Post SAC
	6.4	mITT		Boxplot of Fibrinogen over Time for Subjects with Pneumonia	Screening, Baseline, Day 84 and 168 Subjects who have an event in the 'Infective pneumonia' SMQ	Post SAC

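### The pneumonia displays do not separate values taken before onset from values taken after it, and the one on-treatment panel pairing neutrophils with trough is almost wholly post-onset

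*SAP*

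**What the plan says.** Six planned outputs link pneumonia to a laboratory measure or to exposure.

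- **Figure 5.2** (SAP 14.11.11) is a scatter plot, by day, of neutrophil count and CRP against trough danirixin concentration. The instruction is "Highlight subjects with an on-treatment event in the 'Infective pneumonia' SMQ", followed by "Add footnote 'Note: Pneumonia may have occurred at any time during the study".
- **Figure 3.5** (SAP 14.11.8) is titled "Plot of Mean (95% CI) Neutrophil Counts over Time for Subjects with Pneumonia".
- **Tables 6.3 and 6.4** (SAP 14.11.12) begin with "Summary of C-reactive Protein (CRP) for Subjects with Pneumonia"; Table 6.4 does the same for fibrinogen. Both list Screening, Baseline, Day 84 and Day 168.
- **Two boxplots** (SAP 14.11.13), one for CRP and one titled "Boxplot of Fibrinogen over Time for Subjects with Pneumonia", use the same visits.

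SAP Section 11 defines the biomarker subset as "also for the subset of subjects who have an event in the 'Infective pneumonia' SMQ", with no condition on when the event began. All six outputs are labelled Post SAC. Fibrinogen appears only in Table 6.4 and its boxplot, and trough only in Figure 5.2.

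Onset dates are collected and already used. SAP 14.4.1.3 classifies an event as on-treatment from its onset date, and Table 3.15 splits pneumonia by inhaled corticosteroid use at onset.

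**The concern.** The host-defence risk in Protocol 3.3.1 raises a question of sequence: does a fall in neutrophils, or a high exposure, come before an infection? An ever/never flag applied to values at fixed visits cannot answer it, because samples from before and after the event carry the same mark.

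The event can also change the measurements. Protocol 9.4.5 lists "Elevated white blood cell count (WBC" among the confirming signs of pneumonia, and Protocol 8.1.4 allows study treatment to be interrupted during a hospitalisation, which would lower a trough. A value taken after onset may therefore partly reflect the infection or its management.

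The stake is modest but real. SAP Section 12 makes a PK/PD dataset depend on what the graphical assessment shows, and Protocol 5.4 expects the study to inform the therapeutic index.

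**Working it through.** The plan states no event count, power or precision for these displays, so there is no sponsor figure to reproduce. The check combines the visit schedule with an assumed distribution of onset.

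**Inputs** (Protocol Table 1 and its PK footnote; Day 1 is before the first dose):

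| Measure | Scheduled days, Day 1 to Day 168 |
|---|---|
| Neutrophils (haematology) | 1, 28, 168 |
| CRP, fibrinogen | 1, 84, 168 |
| Trough danirixin | 1, 56, 84, 168 |

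The on-treatment window for events runs to treatment stop + 3 days (SAP 14.4.1.3). Unscheduled values (SAP 14.5.2) and Early Withdrawal values (SAP 14.7.1) are kept out of summaries and figures, apart from worst-case-type assessments and, for unscheduled values, baseline.

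**Assumption.** Onset is uniform over Days 2-168 (167 days). The range runs from linearly front-loaded (weight 169 - d) to linearly back-loaded (weight d).

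**Step 1: shared visits.** Neutrophils and trough coincide on Days 1 and 168, so the only on-treatment neutrophil panel in Figure 5.2 is Day 168. CRP and trough coincide on Days 1, 84 and 168.

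**Step 2: flagged cases with onset by Day 168 (completers).** With onset up to Day 168, 167/167 = 100%. With the window extended to Day 171:
- uniform: 167/170 = 98.2%
- back-loaded: (sum of 2 to 168)/(sum of 2 to 171) = 14,195/14,705 = 96.5%
- front-loaded: almost 100%

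The result, 96-100%, hardly depends on the assumption.

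**Step 3: cases with onset by Day 84 (CRP panel).**
- uniform: 83/167 = 49.7%
- back-loaded: 3,569/14,195 = 25.1%
- front-loaded: 10,458/14,028 = 74.6%

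**Step 4: age of the last scheduled count before onset.** Onset on Days 2-28 leaves only Day 1 (gaps of 1 to 27 days). Onset on Days 29-168 leaves Day 28 (gaps of 1 to 140 days).
- Share with onset on Days 29-168: 140/167 = 84% (range 70-97%).
- For a gap g of 27 days or more, 27 + g of the 167 onset days have a gap of at most g. Half of 167 is 83.5, reached at g = 57. The median gap is about 57 days (range 25-91).
- Share with a count in the preceding 28 days: (27 + 28)/167 = 33% (range 11-55%).
- For CRP, 2g reaches 83.5 at g = 42, a median gap of about 42 days (range 32-52).

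**Step 5: cases with no scheduled on-treatment value before onset.**
- neutrophils: 27/167 = 16%
- trough: 55/167 = 33%
- CRP and fibrinogen: 83/167 = 50%
- same-day neutrophil and trough pair: 167/167, all of them

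A rule keeping only same-visit, on-treatment, pre-onset values would therefore empty the neutrophil panel of Figure 5.2. This shapes the fix.

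**The case against.** The strongest reply is that the plan claims little for these outputs. They are descriptive and Post SAC, SAP Section 12 promises only a graphical assessment, and the Figure 5.2 footnote warns the reader about timing. A reader might infer that post-onset values are presented as explaining the pneumonia. The SAP draws no such inference, so that reading fails.

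A reader might also infer that a preceding low count cannot be seen anywhere. That goes too far. Baseline precedes every on-treatment event, and Day 28 precedes about 84% of onsets under uniform timing. Table 3.19 gives worst-case haematology including unscheduled on-treatment values, and Listings 16 and 24 can be read beside Listings 28, 30 and 58. These routes are partial: the haematology listings cover only values of potential clinical importance or participants who have one, the neutrophil criterion in SAP 14.8.1 is in percent and not absolute count, and a group mean in Figure 3.5 ties no value to an onset.

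Nor does post-onset mean infection-affected. If an infection disturbed values for 14, 28 or 42 days (assumed), the share of cases with onset that recently before Day 168 would be 14/167 = 8%, 28/167 = 17% or 42/167 = 25%. The documents therefore do not show that a drug effect would be masked or reversed.

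Finally, the sparse haematology schedule is itself a limit that no reprogramming removes. This stands, and it belongs in the report as a stated limitation.

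**Conclusion.** The point holds as a gap in how these displays are defined. All six flag or select on having had an event and ignore its timing, although onset dates are available. The only on-treatment neutrophil panel of Figure 5.2 is about 96-100% post-onset among flagged completers and cannot show whether a low count or high exposure came first. CRP at Day 84 mixes about half and half (range 25-75%, depending on the assumed onset distribution).

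It is a low-cost improvement to exploratory outputs. It does not touch the efficacy analyses. A reader might go further and conclude that false reassurance passes straight into the Phase III dose decision. No section ties these figures to that decision, and pneumonia is also summarised by arm in Table 3.14. The number of cases is unknown from the documents, so the practical weight cannot be sized.

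**What to change.** In Figures 3.5 and 5.2, Tables 6.3-6.4 and the two pneumonia boxplots:

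1. Keep all values, but code each pneumonia case's value as before or after onset and give the days from sample to onset. Show cases with a missing onset date separately, since SAP 14.4.1.3 counts them as on-treatment.
2. For each case, also show the last pre-onset value of each measure. Use baseline where no earlier on-treatment value exists, and values from different visits where needed. Compare with same-arm participants without pneumonia by that visit. For trough, mark a Day 1 pre-dose fallback as carrying no exposure information.
3. Include unscheduled and Early Withdrawal values in these displays, as a stated exception to SAP 14.5.2 and 14.7.1. The Early Withdrawal visit schedules haematology, CRP and fibrinogen but no PK sample.
4. List absolute neutrophil counts for every pneumonia case.
5. Replace the Figure 5.2 footnote with the onset-relative definition.
6. State as a limitation that no haematology is scheduled between Day 28 and Day 168, so the last earlier scheduled count will often be old (median about 57 days under uniform onset).

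The cost is SAP wording and extra programming, with no new data and no change to trial conduct. The downside is that pre-onset values will be few and sometimes distant from the event.

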14.11.12. Biomarker Tables

Biomarker: Tables						
StInt No.	SAC No.	Population	IDSL / Example Shell	Title	Programming Notes	Deliverable [Priority]
Biomarkers						
6.1	6.1	mITT	LB1	Summary of C-reactive Protein (CRP) Changes from Baseline	ICH E3	StInt, SAC
6.2	6.2	mITT	LB1	Summary of Fibrinogen Changes from Baseline	ICH E3	StInt, SAC
	6.3	mITT		Summary of C-reactive Protein (CRP) for Subjects with Pneumonia	Screening, Baseline, Day 84 and 168 Subjects who have an event in the 'Infective pneumonia' SMQ	Post SAC
	6.4	mITT		Summary of Fibrinogen for Subjects with Pneumonia	Screening, Baseline, Day 84 and 168 Subjects who have an event in the 'Infective pneumonia' SMQ	Post SAC

## 14.11.13. Biomarker Figures

Biomarker: Figures						
StInt No.	SAC No.	Population	IDSL / Example Shell	Title	Programming Notes	Deliverable [Priority]
Biomarkers						
6.1	6.1	mITT		Boxplot of C-reactive Protein (CRP) by Time and Treatment	Screening, Baseline, Day 84 and 168	StInt, SAC
6.2	6.2	mITT		Boxplot of Fibrinogen by Time and Treatment	Screening, Baseline, Day 84 and 168	StInt, SAC
	6.2	mITT		Boxplot of C-reactive Protein (CRP) over Time for Subjects with Pneumonia	Screening, Baseline, Day 84 and 168 Subjects who have an event in the 'Infective pneumonia' SMQ	Post SAC
	6.4	mITT		Boxplot of Fibrinogen over Time for Subjects with Pneumonia	Screening, Baseline, Day 84 and 168 Subjects who have an event in the 'Infective pneumonia' SMQ	Post SAC

## 14.11.14. ICH Listings

ICH: Listings						
StInt No.	SAC No.	Population	IDSL / Example Shell	Title	Programming Notes	Deliverable [Priority]
Subject Disposition						
	1	ALLSUB	ES7	Listing of Reasons for Screen Failure	Journal Guidelines	SAC
	2	mITT	ES2	Listing of Reasons for Study Withdrawal	ICH E3	SAC
	3	mITT	SD2	Listing of Reasons for Study Treatment Discontinuation	ICH E3	SAC
	4	mITT	BL1	Listing of Subjects for Whom the Treatment Blind was Broken	ICH E3	SAC
	5	mITT	TA1	Listing of Planned and Actual Treatments	IDSL	SAC
Protocol Deviations						
	6	mITT	DV2	Listing of Important Protocol Deviations	ICH E3 Listing also includes analysis population exclusions.	SAC
	7	ALLSUB	IE3	Listing of Screen Failure Subjects with Inclusion/Exclusion Criteria Deviations	ICH E3	SAC
	8	mITT	IE3	Listing of Subjects with Inclusion/Exclusion Criteria Deviations	ICH E3	SAC

ICH: Listings						
StInt No.	SAC No.	Population	IDSL / Example Shell	Title	Programming Notes	Deliverable [Priority]
Populations Analysed						
	9	mITT	SP3	Listing of Subjects Excluded from Any Population	ICH E3 ITT (Strategic interim only), mITT, PP, Symptomatic (Strategic interim only), PK and PK2 population	SAC
Demographic and Baseline Characteristics						
	10	mITT	DM2	Listing of Demographic Characteristics	ICH E3	SAC
	11	miTT	DM9	Listing of Race	ICH E3	SAC
Prior and Concomitant Medications						
	12	mITT	CP_CM3	Listing of Non-COPD Concomitant Medications	IDSL	SAC
	13	mITT	CP_CM3	Listing of COPD Concomitant Medications		SAC
Exposure and Treatment Compliance						
	14	mITT	EX3	Listing of Exposure Data	ICH E3	SAC
EXACT Scores						
	15	mITT		Listing of E-RS: COPD Daily Scores	Total and subscale scores	SAC
Adverse Events						
1	16	mITT	AE8	Listing of All Adverse Events	ICH E3	StInt, SAC
	17	mITT	AE7	Listing of Subject Numbers for Individual Adverse Events	ICH E3	SAC
	18	mITT	AE2	Listing of Relationship Between Adverse Event System Organ Classes, Preferred Terms, and Verbatim Text	IDSL	SAC

ICH: Listings						
StInt No.	SAC No.	Population	IDSL / Example Shell	Title	Programming Notes	Deliverable [Priority]
Serious and Other Significant Adverse Events						
	19	mITT	AE8 / AE8CPa	Listing of Fatal Serious Adverse Events	ICH E3	SAC
	20	mITT	AE8 / AE8CPa	Listing of Non-Fatal Serious Adverse Events	ICH E3	SAC
	21	mITT	AE14	Listing of Reasons for Considering as a Serious Adverse Event	ICH E3	SAC
	22	mITT	AE8 / AECP8	Listing of Adverse Events Leading to Withdrawal from Study / Permanent Discontinuation of Study Treatment	ICH E3	SAC
	23	mITT	AE8 / AECP8	Listing of Drug-Related Adverse Events	ICH E3	SAC
	24	mITT	AE8 / AECP8	Listing of Adverse Events of Special Interest	ICH E3	SAC
Hepatobiliary (Liver)						
	25	mITT	MH2	Listing of Medical Conditions for Subjects with Liver Stopping Events	IDSL	SAC
	26	mITT	SU2	Listing of Substance Use for Subjects with Liver Stopping Events	IDSL	SAC
All Laboratory						
	27	mITT	LB5	Listing of Chemistry Data for Subjects with Any Value of Potential Clinical Importance	ICH E3	SAC
	28	mITT	LB5	Listing of Haematology Data for Subjects with Any Value of Potential Clinical Importance	ICH E3	SAC
	29	mITT	LB5	Listing of Chemistry Values of Potential Clinical Importance		SAC

ICH: Listings						
StInt No.	SAC No.	Population	IDSL / Example Shell	Title	Programming Notes	Deliverable [Priority]
	30	mITT	LB5	Listing of Haematology Values of Potential Clinical Importance		SAC
	31	mITT	LB14	Listing of Laboratory Data with Character Results	ICH E3	SAC
ECG						
	32	mITT	EG3	Listing of All ECG Values for Subjects with Any Value of Potential Clinical Importance		SAC
	33	mITT	EG3	Listing of ECG Values of Potential Clinical Importance		SAC
	34	mITT	EG5	Listing of All ECG Findings for Subjects with an Abnormal ECG Finding		SAC
	35	mITT	EG5	Listing of Abnormal ECG Findings		SAC
Vital Signs						
	36	mITT	VS4	Listing of All Vital Signs Data for Subjects with Any Value of Potential Clinical Importance	IDSL	SAC

